7.5 DATA AND SAFETY MONITORING PLAN

7.5.1 Principal Investigator/Research Team

The clinical research team will meet on a regular basis when patients are being actively treated on the trial to discuss each patient. Decisions about dose level enrollment and dose de-escalation will be made based on the toxicity data from prior patients.

All data will be collected in a timely manner and reviewed by the principal investigator or a lead associate investigator. Adverse events will be reported as required above. Any safety concerns, new information that might affect either the ethical and or scientific conduct of the trial, or protocol deviations will be immediately reported to the IRB using iRIS and to the Sponsor.

The principal investigator will review adverse event and response data on each patient to ensure safety and data accuracy. The principal investigator will personally conduct or supervise the investigation and provide appropriate delegation of responsibilities to other members of the research staff.

7.5.2 Sponsor Monitoring Plan

As a sponsor for clinical trials, FDA regulations require the CCR to maintain a monitoring program. The CCR's program allows for confirmation of: study data, specifically data that could affect the interpretation of primary study endpoints; adherence to the protocol, regulations, and SOPs; and human subjects protection. This is done through independent verification of study data with source documentation focusing on:

- Informed consent process
- Eligibility confirmation
- Drug administration and accountability
- Adverse events monitoring
- Response assessment.

The monitoring program also extends to multi-site research when the CCR is the coordinating center.

This trial will be monitored by personnel employed by a CCR contractor. Monitors are qualified by training and experience to monitor the progress of clinical trials. Personnel monitoring this study will not be affiliated in any way with the trial conduct.

8 STATISTICAL CONSIDERATIONS

The primary objectives of this trial are to assess the safety and tolerability of anetumab ravtansine in patients with unresectable mesothelin expressing previously treated advanced lung adenocarcinoma (stage IIIB or IV), and to determine a preliminary estimate of the response rate of the treatment. Based on the mechanisms of action of anetumab ravtansine, at least minimal tumor expression of mesothelin would be required to anticipate clinical activity. As such, patients to be enrolled on the trial will first be screened for the presence of mesothelin membrane intensity score of 2+ or 3+ (on the 0-3 scale) expressed on the membrane of $\geq 10\%$ of tumor cells. For this assay, subjects must provide sample of archival tumor tissue collected any time before the general screening. Additionally, optional tumor biopsies will be performed before and after 2 doses of anetumab ravtansine.

The first 6 patients enrolled on the trial will receive anetumab ravtansine at a dose of 6.5 mg/kg. If 0 or 1 of the first 6 patients experiences a dose-limiting toxicity (DLT), then the remainder of the patients on the trial will be treated at that dose. If 2 or more patients within the first 6 experience a DLT, then the remaining patients will be treated at 5.5 mg/kg. If at any time during the trial, the cumulative fraction of patients treated at the dose used in the phase II portion of the trial who have a DLT exceeds 1/3, then no further accrual will take place unless a treatment modification is provided via an amendment.

The phase II portion of the trial will be conducted incorporating either the 6 patients treated at 6.5 mg/kg or 5.5 mg/kg as appropriate. Given the expected rarity of responses, the goal would be to determine if using anetumab ravtansine would rule out a 5% response rate and target a rate of 25%. For these patients, the trial will be conducted using a Simon Minimax two-stage phase II trial design in order to rule out an unacceptably low partial response (PR)+ complete response (CR)

rate of 5% (p0=0.05) in favor of an improved response rate of 25% (p1=0.25). With alpha=0.10 (probability of accepting a poor treatment=0.10) and beta = 0.10 (probability of rejecting a good treatment=0.10), this first stage will enroll 13 evaluable patients (including patients treated at the safe dose found in the initial 6 patients), and if 0 of the 13 have a clinical response, then no further patients will be accrued. If 1 or more of the first 13 patients have a response, then accrual would continue until a total of 20 evaluable patients have been treated. As it may take up to several months to determine if a patient has experienced a response, a temporary pause in the accrual may be necessary to ensure that enrollment to the second stage is warranted. If there are 1 to 2 patients with a response out of 20 patients, this would be an uninterestingly low response rate. If there were 3 or more of 20 (15%) who experienced a response, this would be sufficiently interesting to warrant further study in later trials. Under the null hypothesis (5% response rate), the probability of early termination is 51%.

Assessment of serum samples and tumor biopsies will be exploratory and will be summarized descriptively.

The initial portion of the trial may require up to 6 patients who may not be included in the phase II portion if 2 or more of them experience DLTs at 6.5 mg/kg. The phase II portion may require up to 20 evaluable patients. Thus, if 5.5 mg/kg is the selected dose, then up to 26 evaluable patients may be required while if 6.5 mg/kg is selected, only up to 20 evaluable patients may be required. It is anticipated that approximately 50% of screened patients will have <5% mesothelin level and will not be treated on the protocol. Thus, in order to allow for 50% drop-outs for that reason as well as a small number of inevaluable patients, the accrual ceiling will be set at 55 patients. If 2 patients per month enroll on this trial, accrual would be expected to be completed in approximately 28 months.

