2.4 TREATMENT ASSIGNMENT AND RANDOMIZATION/STRATIFICATION PROCEDURES

Cohorts

Number	Name	Description
1	Safety Run-in Cohort,	The first 6 evaluable subjects enrolled in whom the higher of 2 de-escalating doses of anetumab ravtansine will be evaluated in order to determine the recommended phase 2 dose
2	Phase 2 Cohort	Subjects enrolled after the recommended Phase 2 dose has been determined

Arms

Number	Name	Description
1	Safety Run-in Arm	Subjects will be dosed with the higher of the 2 possible anetumab ravtansine doses (dose level 1) evaluated on the study
2	Phase 2 Arm	Subjects will be dosed with anetumab ravtansine at the recommended phase 2 dose (dose level 1 if no more than 1 DLT occurred in the safety run in arm, or at dose level -1 otherwise)

Stratifications

None

Randomization and Arm Assignment

This is not a randomized study. Subjects in Cohort 1 will be assigned directly to Arm 1. Subjects in Cohort 2 will be assigned directly to Arm 2.

2.5 **BASELINE EVALUATION**

Screening evaluations performed within 28 days prior and within 7 days prior to treatment initiation will be used as baseline.

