3 STUDY IMPLEMENTATION

3.1 STUDY DESIGN

This is an open label, single center, phase I/II study of anetumab ravtansine in subjects with mesothelin positive lung adenocarcinoma. During the safety run-in portion of the study a recommended phase 2 dose (RP2D) will be determined in up to 2 dose levels of up to 6 patients each. In the phase 2 portion of the study, 20 evaluable subjects will be evaluated at the RP2D including the 6 subjects treated at this dose during the dose de-escalation study.

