3.1.3 Safety Run-in

The first 6 subjects will be enrolled at dose level 1. If <2 of 6 subjects experience a DLT, dose level 1 will be established as the RP2D and up to 20 evaluable subjects (including the first 6) will be enrolled at this dose level. If 2 or more subjects experience DLT at dose level 1, the RP2D is established at dose level -1 and up to 20 evaluable subjects will be enrolled at this dose level. If a patient did not experience DLT and did not finish treatment, he or she will not be evaluable for toxicity and will be replaced in the dose level. If at any time during the trial, the cumulative fraction of patients treated at the dose used in the phase II portion of the trial who have a DLT exceeds 1/3, then no further accrual will take place unless a treatment modification is provided via an amendment.

Table 3: Dose De-escalation Schedule	
Dose Level	Dose of anetumab ravtansine IV q 3 weeks
Level 1	6.5 mg/kg
Level -1	5.5 mg/kg

Number of Patients with DLT	De-escalation Decision Rule
at Dose Level	
0 or 1 out of 6	This will be the recommended phase 2 dose
$\geq 2 \text{ out of } 6$	The next lower dose level (DL -1) is established as the recommended phase 2 dose

Table 4	. Dece	de accelation	will follow	the wyles	autlined in	the	Table below	
Table 4	: Dose	ue-escalation	will follow	the rules	outimeu m	une	I able below.	

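### The run-in rules misstate who is evaluable for DLT and disagree on whether 5.5 mg/kg has its own six-patient check

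*Combined protocol and SAP*

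**What the plan says.** **Run-in decision.** Six patients start at 6.5 mg/kg, and 0 or 1 DLT in 6 confirms that dose. Otherwise, section 3.1.3 says: "If 2 or more subjects experience DLT at dose level 1, the RP2D is established at dose level -1". Table 4 agrees: "The next lower dose level (DL -1) is established as the recommended phase 2 dose". Section 2.4 describes the run-in cohort as "The first 6 evaluable subjects enrolled in whom the higher of 2 de-escalating doses of anetumab ravtansine will be evaluated", and gives the phase 2 arm "dose level 1 if no more than 1 DLT occurred in the safety run in arm, or at dose level -1 otherwise".

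**Other descriptions of the run-in.** Section 3.1 says of the recommended phase 2 dose: "RP2D) will be determined in up to 2 dose levels of up to 6 patients each". It counts the 20 phase 2 patients as "including the 6 subjects treated at this dose during the dose de-escalation study". The Précis allows up to 12 evaluable run-in patients, and one sentence in section 8 carries forward six patients treated at either dose.

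**Evaluability.** Section 3.1.3 replaces a patient who had no DLT and did not complete treatment, and calls that patient not evaluable for toxicity. Section 3.1.2 defines DLTs by listed events in Cycle 1. Section 3.2 continues treatment until death, progression without clinical benefit, toxicity or another withdrawal criterion. Section 6.3.1 makes every patient evaluable for toxicity from the first dose.

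**Continuing rule.** Sections 3.1.3 and 8 apply, throughout the trial, the condition that "the cumulative fraction of patients treated at the dose used in the phase II portion of the trial who have a DLT exceeds 1/3". If it is met, "then no further accrual will take place unless a treatment modification is provided via an amendment". Neither section gives a minimum number of patients or DLTs.

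**The concern.** The run-in decides which dose the efficacy stage tests, so its denominator must be clear. A replacement rule that can remove only DLT-free patients, for a reason unrelated to the DLT window, pushes the decision towards rejecting 6.5 mg/kg. It also conflicts with section 6.3.1. Because treatment has no fixed end, it leaves unclear when the six-patient decision can be closed.

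If 6.5 mg/kg fails, the team then needs to know whether 5.5 mg/kg is on trial for six patients or already adopted. The documents support both readings. If it is adopted at once, it is the phase 2 dose with nobody yet counted at it, and the one-third rule applies from its first patient. What a single DLT does then depends on how many patients happen to have been dosed.

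**Working it through.** **Figures in the plan.** No operating characteristics are given for the DLT rules, so there is none to reproduce. The one probability in section 8, 51% early termination under the null, does reproduce (0.95^13 = 0.513). It is not affected by this point. The documents state no DLT rate for planning; all rates below are assumptions.

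**1. Evaluability.** Replacing a DLT-free patient keeps all DLTs counted so far and adds one more patient. With r such replacements the decision is in effect taken on n = 6 + r patients, still with a limit of 1 DLT:

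P(reject 6.5 mg/kg) = 1 − (1−p)^n − n·p·(1−p)^(n−1)

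At p = 1/6:
- n = 6: 1 − 0.335 − 0.402 = 0.263
- n = 7: 1 − 0.279 − 0.391 = 0.330
- n = 8: 1 − 0.233 − 0.372 = 0.395

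The same formula gives 0.114, 0.150 and 0.187 at p = 10%, and 0.345, 0.423 and 0.497 at p = 20%. This assumes that the replaced patients had completed Cycle 1 without a DLT.

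**2. Six-patient check at 5.5 mg/kg.**

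| Implies a check | Makes 5.5 mg/kg the phase 2 dose at once |
|---|---|
| Précis: up to 12 run-in patients | 2.4: the run-in arm is the higher dose only |
| 3.1: two levels of up to six | 3.1.3 text and Table 4 |
| 8: six patients at either dose carried forward | 8: after 2 or more DLTs, remaining patients get 5.5 mg/kg |

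The total of 26 evaluable patients in section 8 (6 + 20) fits either column, so it does not settle the matter. No section says what follows 2 or more DLTs in 6 at 5.5 mg/kg.

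**3. One-third rule under the right-hand column.** 1/1 and 1/2 exceed 1/3; 1/3 does not. A halt needs 1 DLT with 1–2 treated, 2 with 3–5, 3 with 6–8, and so on to 7 with 18–20.

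Halt probability by 20 patients comes from an exact patient-by-patient recursion. When patient i is assessed with k more already dosed, the number treated is T = min(i + k, 20), and accrual halts if 3 × DLTs > T. The alternative also requires at least 2 DLTs.

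| k | Rate | Current rule | With 2-DLT minimum |
|---|---|---|---|
| 0 | 10% | 22.2% | 9.6% |
| 0 | 1/6 | 39.6% | 25.6% |
| 1 | 10% | 13.6% | 6.6% |
| 1 | 1/6 | 27.8% | 19.5% |
| 2 | 10% | 4.0% | 4.0% |
| 2 | 1/6 | 13.8% | 13.8% |

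Halts triggered by a single DLT: for k = 0, 1 − (1−p)² = 19.0% and 30.6%; for k = 1, p = 10.0% and 16.7%; for k = 2, none. At 6.5 mg/kg after a passed run-in, the current rule halts with probability 0.8% and 4.6%.

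**4. Net effect of a 2-DLT minimum over the whole trial.** Multiply by the chance of reaching 5.5 mg/kg, which is 0.114 at a 10% rate at 6.5 mg/kg and 0.345 at 20%.
- k = 0: 0.114 × (0.222 − 0.096) = 1.4 points; 0.345 × (0.396 − 0.256) = 4.8 points
- k = 1: 0.114 × (0.136 − 0.066) = 0.8; 0.345 × (0.278 − 0.195) = 2.9
- k = 2: zero

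Cost with k = 0: expected patients treated rise from 6.65 to 9.22 at a true rate of 1/3 and from 4.82 to 7.01 at 40%. With k = 1 they rise from 9.47 to 11.16 and from 7.37 to 8.86.

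**5. Pace.** Section 8 assumes 2 enrolled per month and about 50% screen failure, so about one treated per month against a 21-day cycle. Near-sequential assessment (k = 0) is plausible but not assured, because no staggering is specified.

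**The case against.** **On evaluability**, a sensible team would probably read the clause as meaning completion of Cycle 1. Section 3.1.2 also lets the investigator declare a later event type a DLT, so the window is not absolute. Both are fair, and the 33% and 39.5% are therefore illustrations of literal use. But the later-event provision does not make completing treatment the test of evaluability, and the conflict with section 6.3.1 remains. The error leans towards the lower dose, so it is not a hazard to patients. It can still select the wrong dose for the efficacy stage.

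**On the one-third rule**, a reader might infer that halting on one early DLT is a mistake and that a 2-DLT minimum corrects it. The documents do not support that. The 5.5 mg/kg branch exists only after at least 2 of 6 DLTs one step higher. Section 1.2.3.1 warns of a possible narrow therapeutic index and reports a drug-related hepatic death at 6.5 mg/kg in another study. An early hold is defensible there, an amendment can lift it, and the team discusses each patient (7.5.1).

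Nor should the 22% and 40% be read as the size of the problem. They are conditional on reaching 5.5 mg/kg, and they include halts that a 2-DLT minimum would leave in place. It is also too strong to say that the run-in accepts these rates. It accepts an observed 0 or 1 of 6, and at a true 1/6 it rejects 26% of the time.

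Finally, if the six-patient check is what was intended, the phase 2 dose is arguably not settled during those six and the one-DLT halt may not arise. What stands is that the result of a first DLT turns on enrolment timing, with no statement that this is intended.

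**Conclusion.** The concern holds as two drafting faults in the run-in rules, with one consequence to clarify.

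- **Evaluability.** Replacement is tied to the wrong event. Under literal use and an assumed 1/6 DLT rate, rejection of 6.5 mg/kg rises from 26% to 33% with one replacement and 39.5% with two.
- **Status of 5.5 mg/kg.** The sections contradict each other. The decision rules favour adoption at once, but the Précis, 3.1 and a sentence in 8 point the other way.
- **One-third rule.** Under adoption at once, one DLT halts accrual with one or two treated and not with three. Whether to change that is the sponsor's safety judgement.

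Severity is minor. The 5.5 mg/kg branch is contingent, the hold is reversible, and neither the Simon boundaries (0 of 13, 2 of 20) nor the 20 or 26 patient counts change.

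**What to change.** 1. In 3.1.3, for run-in evaluability and replacement only, replace the condition of not finishing treatment with not completing the Cycle 1 DLT window. Say that the general definition in 6.3.1 is for toxicity reporting.
2. Make the Précis, 2.4, 3.1, 3.1.3 and 8 agree on whether 5.5 mg/kg has a six-patient check. If it does, state what follows 2 or more DLTs in 6.
3. State directly whether a first DLT at 5.5 mg/kg is meant to halt accrual, in terms that do not depend on how many patients have been dosed.

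These cost amendment wording only.

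If the sponsor does not want a first-DLT halt, one option is to require at least 2 DLTs as well as a fraction above 1/3 of those treated. The printed boundary would be 2 DLTs in 2–5 patients, 3 in 6–8, 4 in 9–11, 5 in 12–14, 6 in 15–17 and 7 in 18–20. The price is about 2 to 3 more patients treated on average, with sequential assessment, if the true rate is 1/3 to 40%.

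Combining that option with a six-patient check (stop at 2 or more) gives halts of 12% and 30% at rates of 10% and 1/6 with sequential assessment. With two further patients already dosed it gives 12% and 28%, against 4% and 14% under the current text. The choice should be made with both sets of figures in view.

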9 COLLABORATIVE AGREEMENTS

9.1 COOPERATIVE RESEARCH AND DEVELOPMENT AGREEMENT (CRADA)

The study drug, anetumab ravtansine, will be supplied by the manufacturer, Bayer HealthCare Pharmaceuticals under a CRADA agreement (CRADA #03084) between the manufacturer and the Center for Cancer Research.

10 HUMAN SUBJECTS PROTECTIONS

10.1 RATIONALE FOR SUBJECT SELECTION

This study will be open to all individuals with mesothelin expressing lung adenocarcinoma regardless of gender, ethnicity, or race provided that the aforementioned inclusion and exclusion criteria are met. The selection criteria reflect all available nonclinical and clinical safety experience with anetumab ravtansine. Further, the selection criteria address the potential pharmacokinetics issues that may confound the reliable assessment of the study objective related to the pharmacokinetic drug-drug interaction.

The treatment of men as well as women is justified because of the severity of the underlying neoplastic disease. Men and women who use appropriate contraception or women who are not of child-bearing potential will be enrolled into this study. The proportion of men and women enrolled into the dose-safety run-in cohorts of this study depends only on the availability of subjects at the NIH Clinical Center.

This study will be recruited through internal referral, our local physician referral base, and will be posted on clinicaltrials.gov.

10.2 PARTICIPATION OF CHILDREN

There are no dosing or adverse event data are currently available on the use of BAY 94-9343 / anetumab ravtansine in patients <18 years of age; therefore, children are excluded from this study.

10.3 PARTICIPATION OF SUBJECTS UNABLE TO PROVIDE CONSENT

Adults unable to give consent are excluded from enrolling in the protocol. However re-consent may be necessary and there is a possibility, though unlikely, that subjects could become decisionally impaired. For this reason and because there is a prospect of direct benefit from research participation (section 10.4), all subjects \geq age 18 will be offered the opportunity to fill in their wishes for research and care, and assign a substitute decision maker on the "NIH Advance Directive for Health Care and Medical Research Participation" form so that another person can make decisions about their medical care in the event that they become incapacitated or cognitively impaired during the course of the study. Note: The PI or AI will contact the NIH Ability to Consent Assessment Team for evaluation. For those subjects that become incapacitated and do not have pre-determined substitute decision maker, the procedures described in MAS Policy 87-4 for appointing a surrogate decision maker for adult subjects who are (a) decisionally impaired, and (b) who do not have a legal guardian or durable power of attorney, will be followed.

10.4 EVALUATION OF BENEFITS AND RISKS/DISCOMFORTS

10.4.1 Risks

10.4.1.1 Study Drug

Potential risks of the study include the possible occurrence of any of a range of side effects as listed in section 11.1.2 and the consent document. The procedure for protecting against or minimizing risks will be to medically evaluate patients on a regular basis, provide premedications and supportive therapies as described earlier.

10.4.1.2 Biopsy

Needle biopsy is minimally invasive and is typically a very safe procedure. Depending upon the site being biopsies and the type of biopsy being performed, risks can include infection of the biopsy site, development of a hematoma, and bleeding. Rarely more significant complications can occur when structures near the biopsy target are entered with the needle (e.g. puncture of lung or bowel).

Furthermore, the optional biopsies collected at baseline and after the end of cycle 2 (which may be CT guided) will be for research purposes only. This will result in exposure to approximately 0.27 rem. This amount is below the guideline of 5 rem per year allowed for adult research subjects by the NIH Radiation Safety Committee.

10.4.1.3 Research Blood Sampling

Side effects of blood draws include pain and bruising, lightheadedness, and rarely, fainting.

10.4.2 Benefits

The potential benefit to a patient who enters the study is a reduction in the bulk of his/her tumor, which may or may not have a favorable impact on symptoms and/or survival.

10.5 CONSENT AND ASSENT PROCESS AND DOCUMENTATION

An associate or principal investigator on the trial will inform patients of the purpose, alternatives, treatment plan, research objectives and follow-up of this trial. The patient will be provided an IRB-approved consent for review and signature and his/her questions will be answered. After a decision is made to enroll into the study, a signature will be obtained from the patient at a subsequent visit. The original of the signed informed consent will be placed in the patient's medical record and a copy will be held in the research record.

All patients must have a signed informed consent form and an on-study (confirmation of eligibility) form filled out and signed by a participating investigator before receiving study therapy.

Consent for the optional biopsies on this study will be obtained at the time of the procedure, using the procedure consent. If the patient refuses the optional biopsy at that time, the refusal will be documented in the medical record and in the research record.

